1.5.1 Inclusion Criteria

- Age ≥ 21 years ≤ 70 years
- Regular user of combustible tobacco cigarettes (at least 1 cigarette weekly)
- Regular user of cannabis in any form administered through the pulmonary route (smoking and/or vaping) at least once a week.
- Positive for THC on screening toxicology test
- Willing to abstain from tobacco smoking and all other combustible products (ex: cigars) for 12 hours prior to each outpatient hospital admission.
- Willing to abstain from smoking/ingesting cannabis for 12 hours prior to each outpatient hospital admission.

- Willing to abstain from using any kind of nicotine products for 12 hours prior to each outpatient hospital admission (ex: electronic cigarettes, nicotine replacement therapy).
- Saliva cotinine ≥ 30 ng/mL and/or NicAlert of 6
- Healthy (based on limited physical examination and medical history collected during screening)
 - Heart rate < 105 BPM
 - Systolic Blood Pressure < 160 and > 90 [*considered out of range if both machine and manual readings are above/below these thresholds*]
 - Diastolic Blood Pressure < 100 and > 50 [*considered out of range if both machine and manual readings are above/below these thresholds*]
 - Body Mass Index ≤ 38.0
 - Women of child-bearing potential must use an acceptable contraceptive during the study

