5-min BS#3	~8:50	5-MIN POST-SCV; Blood Sample #3 and Questionnaire Packet #2 
 • BLOOD sample #3 (5-min after last puff) • BLOOD sample, catecholamines • 5-min HEART RATE, 5-min SKIN TEMPERATURE TEST, Core body temperature • Questionnaire packet between 5-min and 15-min blood sample. CRC will administer.
	~8:55	10-min HEART RATE 
 • Questionnaire packet #3
15-min BS#4	~9:00	15-MIN POST-SCV; Blood Sample #4 
 • BLOOD sample #4 (15-min after last puff) • 15-min HEART RATE, 15-min SKIN TEMPERATURE TEST, Core body temperature • Questionnaire packet #4
	~9:05	20-min HEART RATE 
 • Questionnaire packet #5
	~9:10	25-min HEART RATE 
 • Questionnaire packet #6
30-min BS#5	~9:15	30-MIN POST-SCV; Blood Sample #5 
 • BLOOD sample #5 (30-min after last puff) • 30-min HEART RATE, 30-min SKIN TEMPERATURE TEST, Core body temperature
45-min BS#6	~9:30	45-MIN POST-SCV; Blood Sample #6 
 • BLOOD sample #6 (45-min after last puff)
55-min	~9:40	
 • Questionnaire packet #7
	~9:45	60-MIN POST-SCV; Blood Sample #7

1-h BS#7		
 BLOOD sample #7 (1-h after last puff) 1-h HEART RATE, 1-h SKIN TEMPERATURE TEST, Core body temperature
85-min	~10:00	
 Questionnaire packet #8
90-min BS#8	~10:15	90-min POST-SCV; Blood Sample #8 
 BLOOD sample #8 (90-min after last puff) 90-min HEART RATE, 90-min SKIN TEMPERATURE TEST, Core body temperature
2-h BS#9	~10:45	120-MIN POST-SCV; Blood Sample #9 
 BLOOD sample #9 (120 min after last puff from THC1) 2-h HEART RATE, 2-h SKIN TEMPERATURE TEST, Core body temperature
3-h BS#10	~11:45	180-MIN POST-SCV; Blood Sample #10 
 BLOOD sample #10 (180 min after last puff) 3-h HEART RATE, 3-h SKIN TEMPERATURE TEST, Core body temperature Light lunch at noon
6-h BS#11	~14:45	360-MIN POST-SCV; Blood Sample #11 and Questionnaire Packet #4 
 BLOOD sample #11 (2 h after last puff) 6-h HEART RATE, 6-h SKIN TEMPERATURE TEST, Core body temperature Nurses will administer Questionnaire Packet #9
6-h US#2	~14:55	6-h URINE SAMPLE (6-h post SVC)

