6.3 DATA ANALYSIS

The study is not hypothesis-driven but will provide valuable data to guide future research as well as provide needed data on THC delivery and effects from vaping. Variables of interest include amount of THC inhaled, amount exhaled, and amount retained; pharmacokinetic parameters for THC, 11-OH-THC, and nicotine, the psychoactive compounds; heart rate and blood pressure change; and subjective effects.

Delivered and Retained Doses: Delivered THC and nicotine doses are estimated as the change in e-cigarette weight \times concentration of THC or nicotine in e-liquid. The amount of THC or nicotine systemically retained is estimated as delivered dose minus amount in gas traps.

THC, 11-OH-THC, and Nicotine Pharmacokinetics: Pharmacokinetic parameters will be estimated from blood THC and 11-OH-THC and plasma nicotine concentrations using Phoenix WinNonlin 6.3 (Pharsight Corporation, Mountain View, CA). Time to max concentration (T_{max}), max concentration (C_{max}), and area under the blood/plasma concentration-time curves (AUC) will be estimated using a non-compartmental model and trapezoidal rule. C_{max} , and $AUC_{0 \rightarrow \infty}$ will be adjusted for baseline nicotine levels.

Averages and 95% confidence intervals will be computed by e-liquid type (THC only or

THC+nicotine). Although this study is not hypothesis-driven, we will use mixed model analysis of variance (ANOVA) to assess differences in these variables between e-liquids type. Models will include sex as a covariate.

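### Section 6.3 names only AUC0–∞ and corrects the baseline only for nicotine; with sampling ending at 6 h in regular cannabis users, THC exposure may be unstable and inflated

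*Combined protocol and SAP*

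**What the plan says.** Section 6.3 lists among its variables "pharmacokinetic parameters for THC, 11-OH-THC, and nicotine, the psychoactive compounds". It then says that the "area under the blood/plasma concentration-time curves (AUC) will be estimated using a non-compartmental model and trapezoidal rule", without giving an interval. The next sentence says that Cmax and AUC0–∞ "will be adjusted for baseline nicotine levels". That is the only place where an AUC interval appears. There is no rule for the terminal slope, no limit on extrapolation, no AUC to the last sample, and no baseline correction for THC or 11-OH-THC.

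The visit schedule in section 3.4.1(c) and the blood table in section 3.4.3 set a pre-dose sample (B1) and samples at 2, 5, 15, 30, 45, 60, 90, 120, 180 and 360 min. The last two rows are "180-MIN POST-SCV; Blood Sample #10" and "360-MIN POST-SCV; Blood Sample #11 and Questionnaire Packet #4". A THC tube is drawn at every time, B1 included, on all three study days.

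Section 1.5.1 requires at-least-weekly inhaled cannabis use, the criterion "Positive for THC on screening toxicology test", and willingness to abstain from cannabis for 12 h before each admission. Section 1.4.1 allows visits 48 h apart.

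**The concern.** AUC0–∞ is the trapezoidal area to the last sample plus a tail equal to the last concentration divided by the fitted terminal slope. The late samples are at 2, 3 and 6 h, so the slope has about three points behind it and the final one dominates. If THC declines slowly, the tail is a large and noisy part of the result.

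THC already in blood before the session adds area to every sample. It also flattens the fitted slope, which enlarges the tail again. The plan corrects for this with nicotine only.

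At stake are the descriptive estimates of systemic THC exposure under Aim 1, and the comparison of cannabis alone (C) with cannabis plus tobacco (C+T). Section 6.3 reports these as means, 95% confidence intervals and a mixed-model ANOVA, from 14 participants.

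**Working it through.** The plan gives no half-life, extrapolated share or precision target, so there is no figure of its own to reproduce.

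**Inputs from the documents.** Sampling times are as above. The session ends at about 8:45 and sample 11 is at 14:45, which is 6 h. One bullet in the same row reads "BLOOD sample #11 (2 h after last puff"; I use 360 min because the row title, the clock time and section 3.4.3 agree on it.

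**Assumptions.** Bi-exponential decline with the peak at time 0, a distribution half-life of 10 min, a terminal fraction p of 1–10% of peak, terminal half-lives h of 2–24 h, 15% error per sample, and the slope fitted to the last three samples.

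**Step 1: share of the area beyond 6 h.** With peak = 100, k₁ = ln2/(1/6 h) = 4.159 per h and k₂ = ln2/h, the fast phase has area 100(1−p)/k₁ and the terminal phase 100p/k₂. The area beyond 6 h is, in effect, (100p/k₂)·2^(−6/h).

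- h = 6 h, p = 10%: 90/4.159 = 21.6; 10/0.1155 = 86.6; share = 43.3/108.2 = 40%.
- h = 6 h, p = 1%: 23.8 + 8.66 = 32.5; share = 4.33/32.5 = 13%.
- h = 12 h, p = 10%: 21.6 + 173.1 = 194.8; share = 122.4/194.8 = 63%.

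| Terminal half-life | Share beyond 6 h (p = 1–10%) |
|---|---|
| 2 h | 1–7% |
| 4 h | 7–26% |
| 6 h | 13–40% |
| 12 h | 30–63% |
| 24 h | 50–79% |

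**Step 2: stability of the slope.** The times 2, 3 and 6 h have mean 3.667 h and Sxx = 2.778 + 0.444 + 5.444 = 8.667. The leverage of the 6-h sample is 1/3 + 5.444/8.667 = 0.96. The slope's standard error is 0.15/√8.667 = 0.051 per h. At a 12-h half-life the true slope is 0.0578 per h, or 1.13 standard errors, so the fitted slope is zero or rising in about 13% of sessions. At 24 h it is 0.0289 per h, or 0.57 standard errors, giving about 28%. Simulation over the full range of p gives 11–13% and 25–28%.

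**Step 3: noise in the AUC.** The simulated log-SD of AUC0–∞ is about 0.22–0.40 at 6 h and 0.49–0.73 at 12 h. A few near-zero slopes raise these figures; interquartile-based values are 0.10–0.24 and 0.22–0.49. For AUC0–360 min the log-SD is about 0.05–0.07.

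As an illustration, take a paired log-scale contrast with n = 14. Assay and slope noise alone gives a 95% half-width of 2.160·√(2/14)·SD = 0.816·SD. An SD of 0.40 gives a factor of exp(0.327) = 1.39, 0.24 gives 1.22, and 0.05 gives 1.04.

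**Step 4: uncorrected residual THC.** Assume a residual of 1–2% of peak, declining with a 24-h half-life. A 2% residual adds 2·(1−2^(−6/24))/0.0289 = 11.0 to the area up to 6 h.

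- p = 2%, h = 2 h: base area to 6 h = 23.6 + 5.05 = 28.6; inflation 11.0/28.6 = 39%.
- p = 10%, h = 12 h, 1% residual: base area 21.6 + 50.7 = 72.3; inflation 5.5/72.3 = 8%.

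Over p = 2–10% and h = 2–12 h, AUC0–360 min is inflated by about 8–39% and AUC0–∞ by about 12–100%. Cmax rises only by about the residual itself, 1–2%.

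**Step 5: the opposite error.** In tri-exponential examples with a 24-h final phase, the three-point slope gives an apparent half-life of only 1.7–3.4 h. The reported extrapolated share is 4–18% while the true share is 31–59%.

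**The case against.** The strongest reply has five parts.

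- **AUC0–∞ stands in a sentence about nicotine.** The sentence that defines AUC for all analytes gives no interval and would also fit AUC to the last sample. This stands: for THC the infinite interval is an inference. But no other interval is named, so otherwise the THC interval is undefined, and the same edit settles both.
- **No half-life is given.** A reader might infer that THC exposure would be mostly extrapolation. The documents do not support that. In the table above the share passes 50% only at 12 h with a larger terminal fraction, or at about 24 h. At a 2-h half-life it is negligible.
- **Residual THC is not shown.** The toxicology criterion is a urine test at screening, which shows past use rather than blood THC before dosing. This stands as to proof, and the 1–2% is assumed. Weekly or more frequent use with 12-h abstinence still makes it plausible, and B1 will measure it.
- **Each participant is their own control.** Similar residuals would partly cancel between C and C+T. This stands for differences in AUC0–360 min. It does not help the product-specific means. A ratio R is still pulled to (R+f)/(1+f): an assumed R of 1.25 with f = 0.39 becomes 1.64/1.39 = 1.18.
- **The consequence is limited.** The study is declared not to be hypothesis-driven, and the samples allow a later re-analysis. This lowers the stakes. It also means that the fix costs almost nothing. A reader might also infer that participants would be dropped when the slope cannot be fitted; under the planned mixed model, that session's value is lost, not necessarily the participant.

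**Conclusion.** The point holds in a limited form. The plan does not name an AUC interval for each analyte. The one interval it names depends on a terminal slope that the sampling supports poorly, and the baseline correction omits the two cannabinoids.

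How much this matters depends on the THC half-life and terminal fraction, which the documents do not give. At a half-life of 2 h the choice of interval hardly matters. At 6–12 h the extrapolated share is roughly 13–63%, and AUC0–∞ is several times noisier than AUC0–360 min, with a smaller gap on the interquartile measure. The missing THC correction matters for either interval if residual THC reaches 1–2% of peak; its effect on Cmax is small.

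This is a cheap improvement rather than a flaw that undermines the study. Confidence is medium.

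**What to change.** In section 6.3:

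1. Make AUC0–360 min the exposure measure for THC, 11-OH-THC and nicotine.
2. Apply the pre-dose (B1) correction to THC and 11-OH-THC as well as nicotine, for both Cmax and AUC, and state the formula. Subtracting a constant B1 is simple. If the residual declines with a 24-h half-life, a constant 2% removes 12.0 where 11.0 is due, a small over-correction. THC tubes are also drawn on the tobacco-only day, so that day can show how residual THC behaves over 6 h.
3. Report AUC0–∞ only as secondary, with the slope rule and the extrapolated percentage, and only where that share is small (for example 20% or less). A low reported share is not proof of a short tail: all the shares of 4–18% in step 5 would pass this limit.
4. Reconcile the two times given for blood sample 11 in section 3.4.1(c).

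No new samples or visits are needed. The cost is that AUC0–360 min omits exposure after 6 h, which the report should say. It also keeps the 3-h gap: the linear trapezoid overstates the 3–6 h segment by about 1% at a 6-h half-life, 4% at 3 h and 15.5% at 1.5 h.

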3.4 PHARMACOKINETIC STUDY: Outpatient Visits

3.4.2 Protocol for Outpatient Study

3.4.1(a) Marijuana preparation

Cannabis leaf material (11.7% THC) obtained from NIDA will be stored frozen in a locked room in the Zuckerberg San Francisco General Hospital Pharmacy. When a participant is randomized, the pharmacy will dispense of 250 mg of cannabis (this includes a back-up supply of 125 mg). All cannabis will then be stored in the freezer compartment of the medication refrigerator in the medication room of the Clinical Research Services Ward 5B.

Cannabis material to be used by a study participant will be humidified 24-36 hours before use. Using a petri dish placed at the bottom of the desiccator, 2 centrifuge tubes, each filled with sodium chloride solution, will be emptied into the dish. Cannabis cigarettes will be placed on the desiccator platform and maintained at room temperature overnight, which is expected to raise the moisture of the cannabis cigarettes by 3 to 5%. Cannabis material will be used within one hour after removal from the humidifier.

3.4.1(b) Hospital Admission Protocol

Before arrival to the hospital, the study co-I or CRC will meet the participant to collect a urine sample for drug testing. Only when it is confirmed that the participant is negative for all drugs other than cannabis, will we admit him/her on the research ward.

Upon arrival at the research ward, the following procedures will occur:

1. Nurses will ask the participant when they last smoked, vaped, or used THC.
 - If the participant smoked cigarettes or vaped e-cigarettes after 10pm the night before either admission, they will be dismissed from the study.
2. An expired CO test will be administered. If their CO reading is greater than or equal to 5 ppm, they will either be dismissed from the study or procedures will be delayed depending on PI discretion.
3. A pregnancy test will be administered to female participants. If the pregnancy test is positive, they will be dismissed from the study.
4. If the participant is female, the pregnancy test will also serve as the voided urine. If the participant is male, they will provide urine sample for discard.

3.4.1 (c) Outpatient Study Protocol

Samples	Time	Activity
STUDY DAY 1 (same procedures as Study Days 2 & 3)		

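### Section 6.3 baseline-adjusts Cmax and AUC for nicotine only, so residual THC and 11-OH-THC stay in the absolute exposure estimates of regular cannabis users

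*Combined protocol and SAP*

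**What the plan says.** **Analysis.** Section 6.3 states that "Pharmacokinetic parameters will be estimated from blood THC and 11-OH-THC and plasma nicotine concentrations", using a non-compartmental model and the trapezoidal rule. The next step is that Cmax and AUC0-inf "will be adjusted for baseline nicotine levels". No section states a baseline adjustment for THC or 11-OH-THC. Section 6.3 also lists "heart rate and blood pressure change; and subjective effects", so the cardiovascular variables are already framed as change. The point here concerns the pharmacokinetic parameters.

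**Population.** Section 1.5.1 requires each participant to be a "Regular user of cannabis in any form administered through the pulmonary route (smoking and/or vaping) at least once a week" and "Positive for THC on screening toxicology test".

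**Sampling.** The table in section 3.4.3 has a THC tube at all 11 times on Study Days 1, 2 and 3: at 8:20 before vaping, then from 2 to 360 minutes afterwards. The tobacco-only day has the same THC series.

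**Abstinence and admission.** Section 1.5.1 asks that participants be "Willing to abstain from smoking/ingesting cannabis for 12 hours prior to each outpatient hospital admission". In section 3.4.1(b), "Nurses will ask the participant when they last smoked, vaped, or used THC", but the stated consequence covers tobacco and e-cigarettes only: "If the participant smoked cigarettes or vaped e-cigarettes after 10pm the night before either admission, they will be dismissed from the study". An expired CO of 5 ppm or more leads to dismissal or delay at PI discretion. The urine drug test exempts cannabis.

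**The concern.** The plan accepts that regular users arrive with a drug level that the session did not produce, and corrects for it when the drug is nicotine. The same reasoning applies to THC and to its metabolite in people selected for being THC-positive. Without a correction, Cmax and AUC contain the session's contribution plus whatever was there before.

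Aim 1 is to characterise THC delivery and systemic exposure, so the absolute estimates matter in their own right. That the study is declared not hypothesis-driven does not lessen this: in a descriptive study, an inflated mean with its confidence interval is the reported result. AUC is more exposed than Cmax, because vaped THC peaks sharply and briefly while a residual adds area over the whole 6 h.

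**Working it through.** There is no plan figure to reproduce: the documents give no THC concentrations and no power calculation. What follows is a range on stated assumptions.

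**Inputs from the protocol.** Sampling at 0, 2, 5, 15, 30, 45, 60, 90, 120, 180 and 360 min (3.4.3); session at about 8:40 and arrival at about 7:00 (3.4.1(c)); 12 h abstinence (1.5.1). Compliant last use is therefore 7 PM, which is 13 h 40 min (820 min) before the session. Use at 5 AM is 3 h 40 min (220 min) before it.

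**Assumed session profile (Cmax = 1).** A linear rise to 1 at 2 min, then A·2^(−(t−2)/7) + B·2^(−(t−2)/h), with t in minutes and A + B = 1. The terminal half-life h is 1.5 or 3 h, and B is set so that 5% or 20% of Cmax remains at 60 min.

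**Step 1: residual from an earlier dose of session size.** Shift the same profile back by 820 or 220 min. Example for h = 3 h and 20% at 60 min, where B = 0.247: p = 0.247 × 2^(−818/180) = 1.06% of Cmax for 7 PM, and 0.247 × 2^(−218/180) = 10.7% for 5 AM.

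**Step 2: added area.** A residual p that declines with half-life h adds p × G to the trapezoidal AUC 0-6 h. On these sampling times G = 2.100 h for h = 1.5 h and 3.293 h for h = 3 h. A flat residual adds p × 6 h. Dividing by the session's own AUC gives the relative excess:

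| h; left at 60 min | Session AUC 0-6 h (Cmax·h) | 7 PM: p, excess | 5 AM: p, excess | Flat 2%: excess |
|---|---|---|---|---|
| 1.5 h; 5% | 0.341 | 0.01%, 0.1% | 1.4%, 8.4% | 35.2% |
| 1.5 h; 20% | 0.792 | 0.06%, 0.2% | 5.8%, 15.3% | 15.1% |
| 3 h; 5% | 0.382 | 0.25%, 2.2% | 2.5%, 21.9% | 31.4% |
| 3 h; 20% | 0.966 | 1.06%, 3.6% | 10.7%, 36.4% | 12.4% |

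The excess in Cmax is about p itself. Even the 36.4% case raises Cmax by only about 11%.

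**Step 3: one visit or all visits.** The 5 AM figures apply to an affected visit. With 14 participants and equal session AUCs, one such visit moves a condition mean by at most 36.4%/14 = 2.6%. A slow residual from regular use would be present in many participants at once and would not be diluted in this way.

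**Step 4: comparison of the two cannabis conditions.** Let S be the session AUC on cannabis alone, R·S that on cannabis plus tobacco, and r an equal residual on both days.
- Difference: (R·S + r) − (S + r) = (R − 1)·S, so the residual cancels.
- Ratio, with x = r/S: (R + x)/(1 + x). At x = 0.036, a true 0.80 reads 0.807. At x = 0.364, 0.80 reads 0.853 and 1.25 reads 1.183.

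**Step 5: does the form of the correction matter?** Suppose the residual is really flat at 2% but is subtracted as if it declined with the session half-life. The part removed is 2.100/6 = 35% or 3.293/6 = 55%. The excess left is 35.2 − 12.3 = 22.9% in the first row and 12.4 − 6.8 = 5.6% in the last. The decay assumption has to be stated and checked.

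**The case against.** **Abstinence is well supported.** It is an eligibility criterion, is asked about in the phone script (3.2.1), is repeated at orientation and at discharge, and is tied to a bonus of $40 per day (1.7.1). A breach that harms the data would be recorded and reported as a protocol violation under section 5.4. On the fast-clearance assumption a compliant participant adds under 4% to AUC 0-6 h. This stands, and it is why the small figure belongs first. It does not cover a residual that declines slowly in regular users, where compliance alone would not protect the estimate.

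**AUC might be thought to nearly double.** A reader could take pre-dose THC at 10% of Cmax, a 3 h half-life and only 5% of Cmax left at 60 min: 0.10 × 3.293/0.382 = 86%. Those assumptions do not fit together. That profile leaves 2.5% after a session-sized dose at 5 AM, so 10% would need about four such doses. The profile that does leave 10.7% adds 36%.

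**A biased comparison of C with C+T might be inferred.** The documents do not support it. Section 6.3 says mixed-model ANOVA will assess differences and names neither a ratio nor a log scale. The sequences in 1.6.2 are cyclic, so C directly follows C+T in 9 of 14 participants and C+T never directly follows C. With visits at least 48 h apart and a half-life of 1.5-3 h, carryover between sessions is negligible.

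**It might be inferred that nothing stops a participant who has just used cannabis.** That goes too far. The CO test can catch recently smoked cannabis, and the e-cigarette rule can be read to include THC e-cigarettes, since section 1.1 says such devices are not restricted to nicotine. What remains is ingested cannabis and cannabis vaped in a loose-leaf device, assuming CO does not register these.

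**Other limits stand.** The THC amounts inhaled, exhaled and retained, listed first in 6.3, do not depend on blood THC. The pre-dose sample also allows correction after the fact, but the choice would then be made with the data in view, and Step 5 shows that the choice matters.

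**Conclusion.** The gap holds. The only baseline adjustment stated in 6.3 is for nicotine, and a plan followed literally leaves residual THC and 11-OH-THC in the absolute Cmax and, above all, AUC.

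The size cannot be derived from the documents. For THC AUC 0-6 h, assuming a half-life of 1.5-3 h and a prior dose equal to the session, the excess is about 0-4% with compliant use and about 8-36% at a visit preceded by use at 5 AM. A flat residual at 2% of Cmax adds about 12-35%. 11-OH-THC was not modelled separately. The effect on the contrast between cannabis conditions is nil for an untransformed difference with equal residuals, and is attenuation if a ratio is reported.

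The admission gap is real but secondary. The textual finding is certain; its practical weight depends on pre-dose THC levels that the study itself will measure. It should be fixed before analysis because the remedy is nearly free.

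**What to change.** **In section 6.3:**
- State that Cmax and AUC for THC and 11-OH-THC are corrected with the 8:20 pre-dose value of the same visit, as for nicotine.
- State the decay assumption for the subtracted baseline, and repeat the analysis under the alternative (flat versus declining). Check both against the participant's own THC curve on the tobacco-only day, which shows how the residual behaves when no THC is given.
- Add a sensitivity analysis that excludes visits with reported cannabis use within 12 h.

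**In section 3.4.1(b), secondarily:** make reported cannabis use by any route within 12 h of arrival a reason to delay or reschedule at PI discretion. The CO rule already allows delay.

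**Cost.** A few sentences. The THC tubes are already drawn and the last-use question is already asked. The admission rule may delay a few visits, which presses on the 47-, 49- and 51-day limits in section 2.1, and it relies on self-report. The correction in 6.3 is therefore the more important change.

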1.2 RESEARCH QUESTIONS

To understand THC pharmacology and safety of cannabis vaping, including the pharmacology and safety of co-administration of nicotine and THC.

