1.3 SPECIFIC AIMS/OBJECTIVES

1. To characterize Δ^9 -tetrahydrocannabinol (THC) delivery, systemic exposure, and effects from vaping THC-containing cannabis leaf alone or cigarette tobacco alone, or the combination of cannabis and tobacco.
2. To assess sympathetic nervous system (SNS) stimulating and subjective SNS-related effects of THC alone compared to nicotine (tobacco) alone or combined to THC and nicotine co-administration.
3. To assess emissions of THC, terpenes, and other compounds from electronic THC delivery devices.

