1.4 STUDY DESIGN

1.4.1 Design Summary

The study is designed as a within-subjects single-blinded crossover study. Fourteen smokers of tobacco cigarettes and cannabis will switch between three conditions, namely: (a) vaping cannabis leaf, (b) vaping tobacco containing nicotine and (c) vaping a combination of cannabis leaf and tobacco containing nicotine. All participants will vape each product with the PAX loose-leaf vaporizer.

PAX vaporizers will be purchased by the study team. The cannabis leaf will be obtained through the National Institute on Drug Abuse Drug Supply Program. The tobacco containing nicotine, used in conditions (b) and (c) will come from commercially available Marlboro brand cigarettes. The same amount of cannabis or tobacco will be used in all conditions.

The study will be conducted during three outpatient visits separated by at least 48 hours. The order of treatment (cannabis leaf, tobacco with nicotine, cannabis leaf & tobacco with nicotine) will be counterbalanced between subjects. Subjects will be blinded to the content of the vaporizer on the study day but will be told during screening that they will vape cannabis alone, tobacco alone, and cannabis plus tobacco with nicotine.

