1.6.2 Subject assignment to conditions

	1	2	3	4	5	6	7	8	9	10	11	12	13	14
Study Day 1	C	T	C+T	C	T	C+T	C	T	C+T	C	T	C+T	C	T
Study Day 2	T	C+T	C	T	C+T	C	T	C+T	C	T	C+T	C	T	C+T
Study Day 3	C+T	C	T	C+T	C	T	C+T	C	T	C+T	C	T	C+T	C

*Where, C is cannabis leaf; T is tobacco cigarettes; C+T is cannabis leaf + tobacco cigarettes. Order of enrolled subjects will be counterbalanced; order is assigned at admission.

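### Section 6.3 groups results by two product types in a three-condition crossover, so tobacco alone has no planned summary and Aim 2's cannabis versus tobacco contrast is not clearly planned

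*Combined protocol and SAP*

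**What the plan says.** Section 1.4.1 describes a within-subject crossover with three conditions: "a) vaping cannabis leaf, (b) vaping tobacco containing nicotine and (c) vaping a combination of cannabis leaf and tobacco containing nicotine". The assignment table in section 1.6.2 gives all three to each of 14 subjects, with the key "C is cannabis leaf; T is tobacco cigarettes; C+T is cannabis leaf + tobacco cigarettes". Section 3.4.1(c) repeats the full set of study-day procedures on the tobacco-alone day.

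The aims in section 1.3 use all three conditions. Aim 1 covers "effects from vaping THC-containing cannabis leaf alone or cigarette tobacco alone, or the combination of cannabis and tobacco". Aim 2 concerns sympathetic nervous system (SNS) effects "of THC alone compared to nicotine (tobacco) alone or combined to THC and nicotine co-administration". The research question in section 1.2 extends to THC pharmacology and safety, "including the pharmacology and safety of co-administration of nicotine and THC".

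Section 6.3 lists among its variables of interest "pharmacokinetic parameters for THC, 11-OH-THC, and nicotine, the psychoactive compounds; heart rate and blood pressure change; and subjective effects". It then states how results are grouped: "Averages and 95% confidence intervals will be computed by e-liquid type (THC only or". The sentence continues on the next line with THC plus nicotine, and the parenthesis closes there, so the two-level list is complete and not cut off. For inference, "we will use mixed model analysis of variance (ANOVA) to assess differences in these variables between e-liquids type". The levels are not restated, and no other section defines the factor.

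**The concern.** The grouping factor does not match the design. For averages and confidence intervals the omission of tobacco alone is explicit. For the ANOVA it follows if the repeated factor name has the meaning given to it one sentence earlier.

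Two questions would be affected.

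- **SNS and subjective effects.** Aim 2 sets THC alone against tobacco alone. A factor without a tobacco-alone level cannot supply that contrast for heart rate, other SNS measures or subjective effects.
- **Nicotine exposure.** With only C and C+T in the factor, nicotine parameters are compared between a condition that supplies no nicotine and one that does. The informative comparison for co-administration is C+T versus T, which shows how adding cannabis changes nicotine exposure. This question comes from Aim 1, the research question in section 1.2 and the listing of nicotine pharmacokinetics in section 6.3. It does not come from the wording of Aim 2.

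The data to answer both would be collected, but the comparisons would have to be chosen outside the plan.

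**Working it through.** The protocol gives no power or sample-size calculation for this analysis, so there is no stated figure to reproduce. The check counts the sessions outside the stated factor and asks which contrasts remain estimable.

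**Sessions, from the table in section 1.6.2**

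| Study day | Subjects on T | Count |
|---|---|---|
| 1 | 2, 5, 8, 11, 14 | 5 |
| 2 | 1, 4, 7, 10, 13 | 5 |
| 3 | 3, 6, 9, 12 | 4 |

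- T sessions: 5 + 5 + 4 = 14. C and C+T also occur 14 times each.
- All planned sessions: 14 subjects × 3 conditions = 42.
- Share with no planned summary: 14/42 = 33%.
- Sessions that supply nicotine: 14 (T) + 14 (C+T) = 28. Share with no planned summary: 14/28 = 50%.

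**Estimable contrasts**

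The table was coded as a model with subject and condition effects. A contrast is estimable if adding it as a row leaves the rank of the design matrix unchanged.

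| Factor levels | Sessions used | C vs C+T | C vs T | T vs C+T |
|---|---|---|---|---|
| C, C+T (as listed in 6.3) | 28 of 42 | yes | no | no |
| C, T, C+T | 42 of 42 | yes | yes | yes |

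**Set against Aim 2**

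Read literally, Aim 2 takes THC alone as reference and names two comparators, giving C versus T and C versus C+T.

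- ANOVA with the two listed levels: C versus C+T is planned and C versus T is not, so 1 of 2 is missing.
- ANOVA with all three conditions: 0 of 2 is excluded, but no pairwise contrast is named, and the 14 tobacco-alone sessions still have no planned summary.

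**The case against.** The strongest counter-case accepts the omission and disputes its reach.

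- **The 33% is too broad.** Tobacco alone supplies no THC, so for THC and 11-OH-THC outcomes the two listed levels are the relevant ones. This stands as a limit: the gap matters for nicotine, heart rate, other SNS measures and subjective effects, and the 50% figure is the apt one for nicotine.
- **The ANOVA part is inferred.** There is no e-liquid in a loose-leaf study, so the wording may be carried over from another design and cannot be followed literally. The inference is acknowledged, which is why both readings are given. Correcting the product name alone would not add the missing level.
- **Aim 2 is loosely worded.** It could mean a comparison of all three conditions, so the denominator of two is a reading and not a protocol figure. That is fair. The other reading also requires a tobacco-alone level.
- **Some SNS measures are not named in section 6.3.** Skin and core temperature and catecholamines are absent from its list of variables. The list is introduced as what the variables include, so it need not be exhaustive, but the revised text should name them.
- **The study is declared not hypothesis-driven and no data are lost.** This lowers the stakes for error rates. It does not excuse the summaries, because averages and confidence intervals are the main output of a descriptive study.

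**Conclusion.** The concern holds and should be fixed. Tobacco alone is left out of the planned averages and confidence intervals: 14 of 42 planned sessions (33%), or 14 of the 28 that supply nicotine (50%). This follows directly from the text.

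The loss of C versus T from the ANOVA, one of Aim 2's two literal contrasts, is conditional on the model using the two levels in the sentence before it. On the wider reading the contrast is possible but unnamed.

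The counts assume the planned 14 subjects with all three days completed; with complete crossovers the fractions are the same for any number of subjects. The consequence is limited to the analysis plan, since tobacco-alone days follow the same procedures as the others.

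**What to change.** In section 6.3, replace the two-level e-liquid factor with study condition (C, T, C+T) in both the summary sentence and the ANOVA sentence. Summarise each condition in which the outcome is meaningful, and name the contrasts by outcome, each with a 95% confidence interval:

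1. THC and 11-OH-THC dose and pharmacokinetics: C+T versus C.
2. Nicotine dose and pharmacokinetics: C+T versus T.
3. Heart rate, the other SNS measures collected (skin and core temperature, blood catecholamines) and subjective effects: a three-level condition factor, reporting C versus T and C+T versus C for Aim 2, with C+T versus T as an additional contrast.

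The cost is analysis text only for measures already scheduled on all three days: nicotine and THC samples, heart rate, skin and core temperature, blood catecholamines and questionnaires.

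Two related points need separate attention. Section 6.3 lists blood pressure change, but the study-day schedule in section 3.4.1(c) shows no blood pressure reading and section 3.3 places it at screening; these sections must be reconciled. The dose formula in section 6.3 also refers to e-liquid concentration and should be rewritten for loose-leaf material before the dose contrasts are run.
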